3.4 Dose Modifications

NOTE: Patients who interrupt trametinib for > 2 weeks will be removed from this subprotocol, unless the interruption was for reduction in LVEF, visual changes or RPED with subsequent recovery as described in corresponding tables below.

All toxicity grades below are described using the NCI Common Terminology Criteria for Adverse Events (CTCAE) version 4.0.

All appropriate treatment areas should have access to a copy of the CTCAE version 4.0. A copy of the CTCAE version 4.0 can be downloaded from the CTEP website (<http://ctep.cancer.gov>).

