
Criteria for discontinuing study drug:
 
When any of the liver stopping criteria below is met, discontinue trametinib
 
 1. ALT \geq 3xULN and bilirubin \geq 2x ULN or $>35\%$ direct bilirubin^{1,2} 2. ALT \geq 3xULN and INR $>$ 1.5, if INR measured² (INR threshold does not apply if subject is on anticoagulant) 3. ALT \geq 5x ULN 4. ALT \geq 3x ULN persists for \geq 4 weeks. However, if ALT was elevated 3-5x at baseline due to liver mets, then this criteria should not be used for treatment discontinuation UNLESS the ALT improves to $<$ 3x ULN and then subsequently rises. 5. ALT \geq 3x ULN and cannot be monitored weekly for 4 weeks. However, if ALT was elevated 3-5x at baseline due to liver mets, then this criteria should not be used for treatment discontinuation UNLESS the ALT improves to $<$ 3x ULN and then subsequently rises. 6. ALT \geq 3x ULN associated with symptoms³ (new or worsening) believed to be related to liver injury or hypersensitivity 	
 Immediately discontinue study treatment. Do not restart/rechallenge unless approved by the subprotocol Study Chair. / Report as SAE if: 1) CTEP-AERS reporting criteria are met, or 2) patients meet criteria 1-2. Perform liver event ASSESSMENT AND WORKUP (see below). Monitor the subject until liver chemistries resolve, stabilize, or return to baseline (see MONITORING below). / 
MONITORING:
 
In patients stopping for criteria 1-2 (with abnormal TB and INR, indicating potentially more significant liver toxicities):
 
 Repeat liver chemistries (ALT, AST, ALK, bilirubin) and perform liver event follow-up assessments within 24 hours. Monitor subjects twice weekly until LFT return to normal/baseline or stabilize. A specialist or hepatology consultation is recommended. 
In patients stopping for criteria 2-6:
 
 Repeat LFT and perform liver event follow up assessments within 24-72 hrs Monitor subjects weekly until LFTs return to normal/baseline or stabilize. 
ASSESSMENT and WORKUP:
 
 Viral hepatitis serology.⁴ Serum CPK and LDH. Fractionate bilirubin, if total bilirubin \geq 2x ULN. CBC with differential to assess eosinophilia. Record clinical symptoms of liver injury, or hypersensitivity on AE CRF. Record concomitant medications (including acetaminophen, herbal remedies, other over the counter medications). Record alcohol use. 
Additional work up for patient stopping for criteria 1-2 (with abnormal TB and INR, indicating potentially more significant liver toxicities):
 
 Anti-nuclear antibody, anti-smooth muscle antibody, Type 1 anti-liver kidney microsomal antibodies, and quantitative total immunoglobulin G (IgG or gamma globulins). Serum acetaminophen adduct HPLC assay (in subjects with likely acetaminophen use in the preceding). If there is underlying chronic hepatitis B (e.g. positive hepatitis B surface antigen): quantitative hepatitis B DNA and hepatitis delta antibody.⁵ Liver imaging (ultrasound, MRI, CT) and /or liver biopsy.

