Grade 1	
 Initiate prophylactic and symptomatic treatment measures^a Use moderate strength topical steroid^b Reassess after 2 weeks 	
 Continue study treatment If rash does not recover to baseline within 2 weeks despite best supportive care, reduce trametinib by one dose level^c
Grade 2	
 Initiate prophylactic and symptomatic treatment measures Use moderate strength topical steroid^b Reassess after 2 weeks 	
 Reduce trametinib by one dose level 
 If rash recovers to \leq grade 1 within 2 weeks, increase dose to previous dose level If no recovery to \leq grade 1 within 2 weeks, interrupt study treatment until recovery to \leq grade 1 Restart trametinib at reduced dose level^c
Grade \geq 3	
 Use moderate strength topical steroids^b PLUS oral methylprednisolone dose pack Consult dermatologist 	
 Interrupt trametinib until rash recovers to grade \leq 1 Restart^c trametinib reduced by one dose level^d If no recovery to grade \leq 2 within 2 weeks, permanently discontinue trametinib

Abbreviations: CTCAE = Common Terminology Criteria for Adverse Events

- Rash prophylaxis is recommended for the first 6 weeks of study treatment
- Moderate-strength topical steroids: hydrocortisone 2.5% cream or fluticasone propionate 0.5% cream
- Approval of subprotocol Study Chair is required to restart study treatment after $>$ 2 weeks of interruption.
- Escalation of study treatment to previous dose level may be considered if no rash is evident 4 weeks after restarting study treatment

Rev. 12/16

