Uncomplicated Diarrhea ^a Grade 3 or 4 Any Complicated Diarrhea ^b	
 Clinical evaluation mandatory Loperamide^c: initially 4 mg, followed by 2 mg every four hours or after every unformed stool; maximum 16 mg/day. Continue until diarrhea free for 12 hours Oral antibiotics and second-line therapies if clinically indicated Hydration: intravenous fluids if clinically indicated Antibiotics (oral or intravenous) if clinically indicated Intervention should be continued until the subject is diarrhea free for ≥ 24 hours Intervention may require hospitalization for subjects at risk of life-threatening complications 	
 Interrupt trametinib until diarrhea resolves to grade ≤ 1 Restart with trametinib reduced by one dose level^d If 3 dose reductions of study treatment are clinically indicated, permanently discontinue trametinib

Abbreviation: CTCAE = Common Terminology Criteria for Adverse Events

- Uncomplicated diarrhea** defined by the absence of symptoms such as, cramping, nausea/vomiting \geq grade 2, decreased performance status, pyrexia, sepsis, neutropenia grade ≥ 3 , frank bleeding, and/or dehydration requiring intravenous fluid substitution
- Complicated diarrhea** defined by the presence of symptoms such as, cramping, nausea/vomiting \geq grade 2, decreased performance status, pyrexia, sepsis, neutropenia grade ≥ 3 , frank bleeding, and/or dehydration requiring intravenous fluid substitution
- Loperamide should be made available prior to start of study treatment so loperamide administration can begin at the first signs of diarrhea
- Escalation of trametinib to previous dose level is allowed after consultation with the Subprotocol Study Chair and in the absence of another episode of complicated or severe diarrhea in the 4 weeks subsequent to dose reduction.

Rev. 12/16

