3.5.5 Trametinib Dose Modification for Toxicities Not Specified in Subsequent Sections

Table 12 Trametinib Treatment Modification for Clinically Significant Toxicities Deemed Related to Trametinib

(This section is not for specific AEs such as hypertension, rash, ejection fraction changes, pneumonitis, diarrhea, liver chemistry, or visual changes. Refer to other sections for these specific AEs).
		
CTCAE v4 Grade	Management Guideline	Dose Modification
Grade 1	Monitor as clinically indicated. Provide supportive care according to institutional standards.	Continue trametinib at current dose level.
Grade 2 (tolerable)		
 Interrupt treatment until resolution to grade 1 or baseline. Upon resolution, restart treatment at current dose level.
Grade 2 (intolerable) and Grade 3		
 Interrupt treatment until resolution to grade 1 or baseline. Upon resolution to baseline or grade 1, restart with one level of dose reduction. If the Grade 3 toxicity recurs, interrupt trametinib; When toxicity resolves to Grade 1 or baseline, restart trametinib reduced by another dose level.
Grade 4		
If event resolves to grade 1 or baseline discuss potential continuation of trametinib with subprotocol Study Chair; if continuation of treatment agreed then restart trametinib at dose reduced by one dose level.
 
If event does not resolve, permanently discontinue trametinib.

Trametinib should be discontinued if treatment delay is \geq 14 days due to toxicities. If the investigator concludes that continued trametinib will benefit a patient, the subprotocol Study Chair may be consulted for the possibility of resuming trametinib, provided that toxicities have resolved to baseline or grade 1.
		

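### The Section 3.4 NOTE removes patients after more than 2 weeks off trametinib, but the rash table provides for restart after more than 2 weeks, and neither is said to govern

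*Protocol*

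**What the plan says.** **General rule.** The NOTE at the head of Section 3.4 states: "Patients who interrupt trametinib for > 2 weeks will be removed from this subprotocol, unless the interruption was for reduction in LVEF". The sentence then adds visual changes and RPED, with recovery as set out in their tables. Those are the only exemptions, and no approval route is offered.

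**Rash, Table 10 (Section 3.5.3).** The third footnote, which corresponds to marker c, states: "Approval of subprotocol Study Chair is required to restart study treatment after $>$ 2 weeks of interruption". Marker c sits on the restart instruction in both rows that interrupt treatment:

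- Grade 2: the dose is first reduced. If the rash has not come down to grade ≤ 1, the row says "within 2 weeks, interrupt study treatment until recovery to" grade ≤ 1, followed by restart at a reduced level. It puts no limit on the length of the interruption.
- Grade ≥ 3: "Interrupt trametinib until rash recovers to grade" ≤ 1, then restart one level lower. The stopping condition is failure to reach grade ≤ "2 within 2 weeks, permanently discontinue trametinib".

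**Other toxicities, Table 12 (Section 3.5.5).** By default the closing row stops trametinib once a toxicity has held it up for at least two weeks, and it then opens an exception. From the day count on, it reads: "14 days due to toxicities. If the investigator concludes that continued trametinib will benefit a patient, the subprotocol Study Chair may be consulted". That consultation is about resuming, and it presupposes a return to baseline or grade 1. The table expressly does not cover rash.

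**The concern.** A patient with rash who is off drug for more than 2 weeks and then recovers falls under two instructions that cannot both be followed. The NOTE ends participation in the subprotocol. The Table 10 footnote makes sense only if restart is still possible at that point. A site that follows the NOTE would remove the patient and would have no reason to approach the Study Chair; a site that follows Table 10 could ask and restart.

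For the same clinical course, then, sites could differ on whether the patient is re-exposed, how long treatment lasts, and whether a discontinuation is counted. The setting is not remote: Section 3.3 places rash in the likely (>20%) column of the adverse event list, and Section 3.5.3 calls it frequent.

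**Working it through.** The protocol gives no figure to reproduce here. The check sets the rules side by side and runs illustrative courses through them; the day counts are chosen only to show that the cases can occur.

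**Step 1: can a rash interruption exceed 2 weeks under Table 10 itself?**

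- *Case A, grade ≥ 3 row.* Rash is grade 3 on day 0, grade 2 on day 14 and grade 1 on day 20. On day 14 the stopping test (no recovery to grade ≤ 2) is not met, because 2 ≤ 2. The restart test (grade ≤ 1) is not met either, because 2 > 1. The interruption therefore continues. On day 20 the restart test is met.
- *Case B, grade 2 row.* Grade 2 rash has not recovered 2 weeks after dose reduction. Drug is then interrupted for 18 days until grade 1. The row has no time limit, so the restart condition is met on day 18.

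The grade 1 row does not interrupt treatment. The case is therefore reachable in 2 of 3 rows.

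**Step 2: apply both rules.**

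| Case | Days off drug | Section 3.4 NOTE | Specific table |
|---|---|---|---|
| A: rash, grade ≥ 3 row | 20 > 14 | Removed | Table 10: restart possible with Study Chair approval |
| B: rash, grade 2 row | 18 > 14 | Removed | Table 10: restart possible with Study Chair approval |
| C: grade 3 toxicity under Table 12, grade 1 at day 18 | 18 > 14 | Removed | Table 12: discontinue by default (18 ≥ 14); Study Chair may be consulted on resuming |

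A and B are direct conflicts. In C the default agrees with the NOTE and only the exception departs from it.

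**Step 3: look for a statement of precedence.**

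- Section 3.5.3 discusses institutional standards that differ from its guidelines; it does not mention the NOTE.
- Table 12 excludes rash, so its Study Chair route cannot settle Cases A and B.
- The list in Section 3.7 applies only where there are no treatment delays from adverse events.

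No other text in the document ranks the NOTE against the tables.

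**Step 4: places where the reach of the NOTE is unclear but there is no contradiction.**

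- Table 7 (liver, Section 3.5.1): "Do not restart/rechallenge unless approved by the subprotocol Study Chair". No time limit is given.
- Table 11 (Section 3.5.4), grade 3 or 4 or complicated diarrhea: restart follows resolution, with no time limit. Its only stopping rule is "If 3 dose reductions of study treatment are clinically indicated, permanently discontinue trametinib". The grade 1 or 2 row does have a limit of more than 14 days, in line with the NOTE.
- Table 8 (QTc, Section 3.5.2) and Scenarios B and C of Table 3 (hypertension, Section 3.4.3.2) also provide for interruption and restart without a limit on its length.

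These tables are silent on duration, so the NOTE can be applied alongside them.

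**Step 5: boundary.** On exactly day 14, the Table 12 limit (≥ 14 days) is reached and the NOTE's limit (> 2 weeks) is not. Both can be followed, so this is a drafting difference only.

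**The case against.** The strongest reply is that the NOTE governs Section 3.4 only. It heads that section, its exemptions are the Section 3.4 tables with 4-week recovery windows (LVEF, visual changes, RPED), and the pneumonitis table in the same section uses 2 weeks, as the NOTE does. Rash and Table 12 fall under Section 3.5, where several tables carry their own delay rules, so the specific table would override the general note.

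That reading is available, but the document does not state it. The NOTE speaks of patients who interrupt trametinib, with no limit by section. It also names its exemptions one by one, which would be unnecessary if every table overrode it.

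A second reply is that the footnote is a restriction, not a permission. It does work as a safeguard. But if every rash interruption beyond 2 weeks already means removal, the footnote has nothing left to regulate.

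Three points on the other side stand. The restart routes in Tables 10 and 12 go through a single role, the subprotocol Study Chair, and a site managing rash will have Table 10 in front of it, which bounds the practical effect. The Table 12 conflict is thin. And the MATCH Master Protocol is not at hand and might contain a general rule, although this subprotocol does not point to it on this matter.

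**Conclusion.** The inconsistency is real and should be fixed. There is one direct conflict, between the Section 3.4 NOTE and Table 10, reachable in two of its three grade rows, and one weaker conflict confined to the exception in Table 12. The conclusion rests on reading the NOTE as written, without an unstated limit to Section 3.4, and on this document alone.

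The number of patients affected cannot be derived, because the document gives no frequency for interruptions longer than 2 weeks. No effect on a primary result is claimed. What is at stake is consistency between sites in re-exposure, treatment duration and the recording of discontinuations.

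**What to change.** Reconcile the Section 3.4 NOTE with Table 10 and Table 12. The amended text should state:

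- which text governs when the NOTE and a toxicity table differ;
- whether Study Chair approval can override removal, and for which toxicities;
- the complete list of exemptions, including whether the NOTE applies where no time limit is set: Table 7 rechallenge, the grade 3 or 4 or complicated diarrhea row of Table 11, Table 8, and Scenarios B and C of Table 3.

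As a minor drafting point, express the limit the same way in the NOTE and in Table 12. Which clinical rule applies is for the sponsor to decide.

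The cost is amendment wording, with no added patients or procedures.

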3.4.1 Dose Modification Guidelines for Trametinib Adverse Events of Special Interest

The dose levels for this study are provided in Table 1.

Dose Levels	Trametinib once daily
Full dose	2 mg
1 st Dose reduction	1.5 mg
2 nd Dose reduction	1.0 mg

Table 1 Dose Level Reduction Guidelines

3.4.2 If an AE resolves to grade 1 or lower (or baseline) and remains grade 1 or lower at the reduced dose level and the subject does not experience any additional AEs requiring dose hold or reductions, then after 4 weeks of the study treatment at reduced dose, the dose of trametinib may be increased one dose level. If a dose reduction below 1 mg once daily for trametinib is required, then trametinib will be permanently discontinued.

3.4.3 Guidelines for Cardiovascular Adverse Events

Cardiovascular adverse events have been seen in subjects receiving trametinib[4]). Guidelines for LVEF decreases and hypertension are provided below.

3.4.3.1 Left Ventricular Ejection Fraction (LVEF)

Decreases of the left-ventricular-ejection-fraction (LVEF) have been observed in subjects receiving trametinib. Therefore, ECHOs (preferred) or a MUGA must be performed for subjects experiencing symptoms concerning for decline in LVEF to assess cardiac ejection fraction. The procedure performed at baseline must be performed at all subsequent visits as outlined in the Time and Events Table (See Section [4.1](#)).

Dose modification guidance and stopping criteria for LVEF decrease are provided (Table 2).

Table 2 Dose Modification Guidelines and Stopping Criteria for LVEF Decrease

Clinic	LVEF-drop (%) or CTCAE grade	Action and Dose Modification
Asymptomatic	Absolute decrease of >10% in LVEF compared to baseline and ejection fraction below the institution's LLN	
 • Interrupt trametinib and repeat ECHO/MUGA within 2 weeks^a • If the LVEF recovers within 4 weeks (defined as LVEF \geq LLN and absolute decrease \leq 10% compared to baseline): 
 - Consult with the subprotocol Study Chair and request approval for restart - Restart treatment with trametinib at reduced dose by one dose level^b - Repeat ECHO/MUGA 2, 4, 8 and 12 weeks after re-start; continue in intervals of 12 weeks thereafter • If LVEF does not recover within 4 weeks 
 - Consult with cardiologist - Permanently discontinue trametinib - Report as SAE - Repeat ECHO/MUGA after 2, 4, 8, 12, and 16 weeks or until resolution - Consult with the subprotocol Study Chair.^c
Rev. Add13	Grade 3: resting LVEF 39-20% or > 20% absolute reduction from baseline	
 • Permanently discontinue trametinib. • Report as SAE • Consult with cardiologist
	Grade 4: resting LVEF < 20%	
 • Repeat ECHO/MUGA after 2, 4, 8, 12, and 16 weeks or until resolution

Abbreviations: CTCAE = Common Terminology Criteria for Adverse Events; ECHO = echocardiogram; GSK = GlaxoSmithKline; LLN = lower limit of normal; LVEF = left ventricular ejection fraction; MUGA=Multi-gated acquisition

- If ECHO/MUGA does not show LVEF recovery after 2 weeks, repeat ECHO/MUGA 2 weeks later.
- Escalation of trametinib to previous dose level can be considered if LVEF remains stable for 4 weeks after restarting of trametinib. Approval from the subprotocol Study Chair is required.
- Symptoms may include: dyspnea, orthopnea, and other signs and symptoms of pulmonary congestion and edema.

3.4.3.2 Hypertension

Increases in blood pressure (BP) have been observed in patients receiving trametinib. Recommendations for BP monitoring and management are provided below.

Monitoring: All BP assessments should be performed under the following optimal conditions:

- The subject has been seated with back support, ensuring that legs are uncrossed and flat on the floor
- The subject is relaxed comfortably for at least 5 minutes

- Restrictive clothing has been removed from the cuff area and the right cuff size has been selected
- The subjects arm is supported so that the middle of the cuff is at heart level
- The subject remains quiet during the measurement.
- In subjects with an initial blood pressure reading within the hypertensive range, a second reading should be taken at least 1 minute later, with the 2 readings averaged to obtain a final blood pressure measurement. The averaged value should be recorded in the eCRF.
- Persistent hypertension is defined as an increase of systolic blood pressure (SBP) > 140 mm Hg and/or diastolic blood pressure (DBP) > 90 mm Hg in three consecutive visits with blood pressure assessments from two readings collected as described above. Visits to monitor increased blood pressure can be scheduled independently from the per-protocol visits outlined in the study calendar. Ideally, subsequent blood pressure assessments should be performed within one week.

Table 3 Management and Dose Modification Guidelines for Hypertension

Management and Trametinib Dose Modification for Hypertension		
Event	Management Guideline	Dose Modification
Definitions used in the table:		
	
 Persistent hypertension: Hypertension detected in two separate readings during up to three subsequent visits. Well-controlled hypertension: Blood pressure of SBP \leq140 mmHg and DBP \leq90 mmHg in two separate readings during up to three subsequent visits. Symptomatic hypertension: Hypertension associated with symptoms (e.g., headache, light-headedness, vertigo, tinnitus, episodes of fainting or other symptoms indicative of hypertension) that resolve after the blood pressure is controlled within the normal range. Asymptomatic hypertension: SBP $>$140 mmHg and/or DBP $>$90 mmHg in the absence of the above symptoms. 	
(Scenario A) Asymptomatic and persistent SBP of \geq 140 and $<$ 160 mmHg, or DBP \geq 90 and $<$ 100 mmHg, or Clinically significant increase in DBP of 20 mmHg (but still below 100 mmHg).	
 Adjust current or initiate new antihypertensive medication(s). Titrate antihypertensive medication(s) during the next 2 weeks to achieve well-controlled BP. If BP is not well-controlled within 2 weeks, consider referral to a specialist and go to scenario (B). 	Continue trametinib at the current dose.
(Scenario B) Asymptomatic SBP \geq 160 mmHg, or DBP \geq 100 mmHg, or Failure to achieve well-controlled BP within 2 weeks in Scenario A.	
 Adjust current or initiate new antihypertensive medication(s). Titrate antihypertensive medication(s) during the next 2 weeks to achieve well-controlled BP. 	
 Interrupt trametinib if clinically indicated. Once BP is well-controlled, restart trametinib reduced by one dose level.^a
(Scenario C) Symptomatic hypertension or Persistent SBP \geq 160 mmHg, or DBP \geq 100 mmHg, despite antihypertensive medication and dose reduction of trametinib	
 Adjust current or initiate new antihypertensive medication(s). Titrate antihypertensive medication(s) during the next 2 weeks to achieve well-controlled BP. Referral to a specialist for further evaluation and follow-up is recommended. 	
 Interrupt trametinib. Once BP is well-controlled, restart trametinib reduced by one dose level.^a
(Scenario D) Refractory hypertension unresponsive to above interventions or hypertensive crisis.	Continue follow-up per protocol.	Permanently discontinue trametinib.
a. Escalation of trametinib to previous dose level can be considered if BPs remain well controlled for 4 weeks after restarting of trametinib. Approval from subprotocol Study Chair is required.		

